#### 7.5.9.4 Bladder Diary

Subjects will complete 72-hour bladder diaries at the required timeframes. The bladder diary is expected to be completed electronically but paper may be used as a backup.

The 72-hour bladder diary will collect voiding frequency (voids), void volume (specified times), urgency, urinary urgency incontinence (UUI) episodes (leaks), activity during UUI (at baseline only), and pad use. Subjects will record events for a consecutive 72-hour period, starting from when they first begin recording events.

Subjects will be trained on proper methods for completing the diary, collecting, and measuring the urine volume, and distinguishing between urge and stress incontinence episodes.

Baseline Bladder Diary: A baseline 72-hour bladder diary will be completed after the subject has stopped OAB medication for period determined appropriate based on type of OAB medication (at least five half-lives) to confirm the UUI inclusion criterion. At the discretion of the investigator, subjects who failed to accurately complete their diary may be allowed to repeat the diary evaluation. Those who failed to qualify after a second diary attempt will be withdrawn from further study participation.

Follow-up Bladder Diaries: Subjects will complete a 72-hour bladder diary prior to each scheduled clinic visit. Voided volume will only be collected at baseline and at Month 6 and 12 clinic visits. The bladder diary will be completed for a consecutive 72-hour period starting 4-7 days prior to each required follow-up visit. If a subject fails to complete the diary before the scheduled visit date, they may start the 72-

Protocol no: NSM-004; Version 21.0 Page 93 of 141 04 Apr 2025
Confidential Neuspera

hour diary within 24-hours of the scheduled visit date. If a subject continues to miss the start of the 72hour diary completion prior to a scheduled visit date, they will be assessed for protocol non-compliance.

If a subject is symptomatic with a UTI prior to beginning or in the middle of a 72-hour bladder diary, it is recommended to the subject start the diary after the subject is asymptomatic after standard-of-care treatment.

Subjects may be requested to complete an additional diary following programming changes to assess the impact of the changes. Subjects completing additional diaries will not need to collect void volume.

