Month 4 Clinic Visit: 120 (-/+ 14) days	
Month 5 Clinic Visit: 150 (-/+ 14) days	
Month 5.5 Telephone Visit	
Month 6 Clinic Visit: 180 (-/+14) days	
Month 9 Clinic Visit: 270 (-/+ 14) days	
Month 12 Clinic Visit: 360 (-/+ 14) days	

Protocol no: NSM-004; Version 21.0 Page 99 of 141 04 Apr 2025 Confidential Neuspera

TABLE 9: VISIT PROCEDURE SCHEDULE - PHASE II

					Post-Implant		Study Exit		
Procedure	Screening / Baseline	Baseline Assess- ment	i- Implant	Clinic Visit (Day 7, 14, 21, 28) & Day 35, 42 (if required)	Clinic Visits Month 2 to 6 Every 3 Months to Month 12, every 6 Months to Month 36	Telephone Visits At 5.5 months.	Unscheduled Follow-up Visit	Device	30-Day Post- Explant F/U
Informed Consent	х								
Inclusion/Exclusion	Х		Х						
Baseline Evaluation (Demographics, Medical History, OAB History, Physical Exam)	Х								
Vital Signs	Х		х	X	X			Х	Х
HbA1c	Х								
Urinalysis	Х								
Pregnancy Test (if applicable)	Х								
Assessment of Subject's Sacral Anatomy	Х								
Urodynamics (within 6 months)	Х								
Cystoscopy (within 6 months)	Х								
OAB Medication Washout (at least 5 half-lives of OAB medications)	х								
Medication Use & Changes (including OAB Medication) & Conservative OAB Therapies Log)	х		Х	Х	Х	Х	х	Х	Х
Body Weight	Х				Month 12, 24, and 36				
Adverse Events	Х		Х	Х	Х	Х	Х	Х	Х
Wound Check				Х					Х
1-3 Day Post Implant Telephone Check				Х					
Neurostimulator position confirmation image			Х	X (Day 28 or Day 42)				Х	
Response Rate Assessment				X (Day 28 and/or 42)					
Therapy Review and Adjust Stimulation				Х	Х				
72-Hour Bladder Diary		X (Voided volume required)		х	X (Voided volumes at Month 6 and 12)				
Stimulation Diary				Х	X (Daily ≤ Month 12 Weekly > Month 12)	Х			
Wexner Scale (if FI)		Х		х	Х				
ICIQ-OABqol, MLUTS/FLUTS		Х			X (Month 3,6,12,24 & 36)				
PGI-I					X (Month 3,6,12,24 & 36)				
Subject User Experience Questionnaire				X (Day 28 or 42)	X (Month 6)				
Device Explant								Х	
Study Exit									Х

Protocol no: NSM-004; Version 21.0 Confidential

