5.6.3.1 Analysis of Secondary Endpoints That May be Used for Labeling Claims

The primary analysis population for the secondary efficacy endpoints that may be used for labeling claims is the mITT analysis set as defined in Section 5.2. Section 5.6.4 describes missing data handling for these secondary efficacy endpoints in the mITT analysis set. These endpoints may also be assessed in other analysis sets without imputation for missing values.

S	tatistical Analysis Plan	Pa	ge 18 of 25
Sponsor	Study		Version
Neuspera	Clinical Study of Neuspera's Implantable Sacral Nerve Stimulation (SNS) System in Patients with Symptoms of Urinary Urgency Incontinence (UUI)		17.0

The type I error for the primary efficacy endpoint and for a subset of secondary endpoints will be controlled via hierarchical testing, in the order listed below.

The following secondary endpoints will be included in a hierarchical analysis of study endpoints and may be intended for labeling claims (all at 6-month visit post-implant follow-up):

- Change from baseline in mean number of UUI episodes
- Change from baseline in ICIQ-OABqol score
- The percentage of subjects who experience an improvement in ICIQ-OABqol of at least 10 points
- Change in urgent episodes per day from baseline. Calculated across all diary episodes with at least mild urgency
- Change in average number of daily voids from in subjects with at least 8 voids at baseline
- Change in fecal incontinence as measured by the Wexner Scale compared to baseline. Calculated in subjects with fecal incontinence.

For the ICIQ-OABqol, analysis will be conducted according to published scoring criteria (Coyne et al., 2002)^{iv}.

The statistical hypothesis tests for continuous endpoints will be based on comparing the mean change scores at 6 months or 12 months to 0. Mathematically, the null and alternative hypotheses are stated as:

Ho: $\mu \le 0$ Ha: $\mu > 0$

The statistical hypothesis test for the categorical endpoint based on UUI episodes will be based on comparing the percentage of subjects with a 50% improvement in UUI symptoms (therapy responders) at 12 months to a null value of 50%. Mathematically, the null and alternative hypothesis are stated as:

Ho: $p \le 0.50$ Ha: p > 0.50

The statistical hypothesis test for the categorical endpoint based on ICIQ-OABqol will be based on comparing the percentage of subjects with at 10 point improvement (the minimally clinically important

S	tatistical Analysis Plan	Pa	ge 19 of 25

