5.6.4 Handling of Missing Data

All attempts will be made to limit the amount of missing data. No attempt will be made to impute missing data for any analyses except for the primary and secondary efficacy endpoints as specified below in the mITT analysis set. If a data point is missing, that data point will not contribute to that portion of the analysis. The number of evaluable observations will be reported in the analysis so that extent of missing data can be assessed.

For the following efficacy endpoints, subjects withdrawing for reasons related to a lack of efficacy or due to an adverse event (including death) will be counted as failures if they do not have evaluable data for the endpoint:

- The percentage of all implanted subjects who experience an improvement in UUI symptoms of 50% or more at 6-month post-implant (primary efficacy endpoint)
- The percentage of all implanted subjects who experience an improvement in UUI symptoms of 50% or more at 12-month post-implant (secondary efficacy endpoint)

For the continuous efficacy endpoints that may be used for labeling claims, no change from baseline values will be assumed for subjects withdrawing for reasons related to a lack of efficacy or due to an adverse event (including death) if they do not have evaluable data for the endpoint.

If data on these endpoints are missing for other reasons (missing diary or ICIQ-OAB questionnaire, subject loss-to-follow-up, etc.), multiple imputation will be used to impute the outcome. Results from the imputed data sets will be combined appropriately to preserve valid inference. A tipping point analysis will also be performed, examining outcomes for the primary efficacy endpoint for all possible permutations of imputed values for missing subjects.

Multiple imputation will be based on the following variables and will use full conditional specification and 100 imputed data sets. Variables to be included in the imputation model include:

- baseline age, investigational site, baseline UUI episodes, and all available follow-up visit UUI
 episodes through 6 months or 12 months (for the primary and secondary efficacy endpoints of
 improvement in UUI)
- baseline age, investigational site, baseline score, and all available follow-up visit scores through 6 months or 12 months (for the remaining secondary efficacy endpoints that may be used for labeling claims)

S	tatistical Analysis Plan	Pa	ge 21 of 25
Sponsor	Study		Version

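### A missing Month 6 ICIQ-OABqol score is imputed without the Month 4 and 5 diaries, so nothing observed after Month 3 informs it; adding the diary counts is a free, optional improvement

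*Protocol*

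**What the plan says.** **Collection.** Protocol Table 9 (Section 7.5.9.16) places the ICIQ-OABqol at the baseline assessment and then at "Month 3,6,12,24 & 36". The diary is far more frequent. Section 7.5.9.4 states: "Subjects will complete a 72-hour bladder diary prior to each scheduled clinic visit". Table 8 includes a Month 4 visit and "Month 5 Clinic Visit: 150 (-/+ 14) days", so a diary is due at both, with no ICIQ-OABqol.

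**Imputation.** SAP 5.6.4 has two variable lists. For the UUI responder endpoints it is "baseline age, investigational site, baseline UUI episodes, and all available follow-up visit UUI" episodes. For the remaining labeling endpoints it is "baseline age, investigational site, baseline score, and all available follow-up visit scores through 6 months or 12 months". Diary counts are named only in the first list.

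**When imputation applies.** SAP 5.6.4: "If data on these endpoints are missing for other reasons (missing diary or ICIQ-OAB questionnaire, subject loss-to-follow-up, etc.), multiple imputation will be used". Subjects who withdraw for lack of efficacy or an adverse event, and have no evaluable data, are instead given no change on the continuous labeling endpoints. The tipping point analysis is specified for the primary efficacy endpoint only.

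**Role of the endpoint.** In SAP 5.6.3.1, "Change from baseline in ICIQ-OABqol score" is second in the hierarchical labeling sequence, tested against a mean of zero. The proportion improving by at least 10 points is third, tested against 50%.

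**The concern.** Multiple imputation is unbiased only if, given the variables in the model, being missing is unrelated to the unobserved outcome. A late diary plausibly relates to both: a subject whose incontinence has returned by Month 5 probably has a worse Month 6 quality-of-life score, and may be less likely to attend. Leaving that diary out weakens the missing-at-random assumption when the trial already holds the information.

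Late loss of response is not far-fetched. The Phase I responder rates in Protocol 3.1.2.1 are 97% at Month 4, 78.6% at Month 5 and 88.5% at Month 6. This is weak support: the figures are interim, and the rate at Month 9 is 100%.

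At stake is a favourable bias in the ICIQ-OABqol labeling endpoints, with no planned sensitivity analysis that would show it. Failure at either step also ends formal testing of the endpoints that follow.

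**Working it through.** **1. What informs the imputed value.** Between baseline and Month 6 there is one ICIQ-OABqol score (Month 3). There are 8 to 10 diaries: Days 7, 14, 21 and 28, Days 35 and 42 if required, and Months 2, 3, 4 and 5. The ICIQ-OABqol model uses none of them. If only the Month 6 questionnaire is missing, the Month 6 diary is available too and is also unused. I read the 6-or-12-month clause as stopping at the endpoint visit. On a wider reading a later Month 12 score could help a subject who skipped one questionnaire, but not one who is lost.

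**2. The plan's threshold.** The documents state 72 of 120 for the primary endpoint. The 10-point responder test has the same null (50%) and one-sided alpha (0.025). Exact binomial, N = 120: P(X ≥ 71) = 0.0274, which fails; P(X ≥ 72) = 0.0177, which passes. The stated 72 reproduces.

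**3. Mechanism in one constructed subject (all inputs assumed).** Month 6 change has mean 25 and SD 20. The subject is +0.5 SD on the Month 3 score and −2 SD on the Month 4–5 diary. Correlations: Month 3 with Month 6 score 0.7, diary with Month 6 score 0.6, diary with Month 3 score 0.4.
- Planned model: mean = 25 + 20 × 0.7 × 0.5 = 32. Residual SD = 20 × √(1 − 0.49) = 14.3. P(change ≥ 10) = Φ(22/14.3) = 0.94.
- With the diary: weights are (0.7 − 0.6 × 0.4)/0.84 = 0.548 and (0.6 − 0.7 × 0.4)/0.84 = 0.381. Mean = 25 + 20 × (0.548 × 0.5 − 0.381 × 2) = 15.2. Residual SD = 20 × √(1 − 0.7 × 0.548 − 0.6 × 0.381) = 12.5. P(change ≥ 10) = Φ(5.2/12.5) = 0.66.

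This is an extreme profile. It shows the direction, not the average effect.

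**4. Average effect in missing subjects (simulation, inputs assumed).** Monthly autocorrelation of response 0.8, diary reliability 0.8, ICIQ-OABqol change SD 20, 8% missing at Month 6, missingness depending on the Month 5 diary. With mean change near 15, P(change ≥ 10) among missing subjects is:

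| Correlation of score with same-visit UUI response | Odds ratio of missing per SD worse diary | True | Planned model | With diary UUI |
|---|---|---|---|---|
| 0.4 | 2.0 | 0.522 | 0.583 | 0.519 |
| 0.5 | 3.3 | 0.441 | 0.559 | 0.443 |
| 0.6 | 3.3 | 0.409 | 0.542 | 0.411 |

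The excess in these rows is 6.1, 11.8 and 13.3 percentage points. Over correlation 0.4–0.6, mean change 15 or 25 and different persistence of the score, it is about 4 to 15 points at odds ratio 2.0–3.3, and only about 2 to 3 points at 1.3.

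**5. Share missing.** In Phase I (Protocol synopsis), 34 subjects were implanted. Of 12 explants, 11 were for unsatisfactory effect, therapy or device performance and one for non-compliance. Of two exits without explant, one was an adverse event and one a loss to follow-up. So 1 or 2 of 34 (2.9% or 5.9%) would clearly reach imputation through study exit. I take 3 to 8%, the upper end allowing for missed questionnaires; the documents give no rate for those.

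**6. Effect on the two tests.**
- Responder test: low end 120 × 0.03 × 0.02 = 0.07; high end 120 × 0.08 × 0.15 = 1.44. That is roughly 0.1 to 1.4 responders.
- Mean change: SE = 20/√120 = 1.83. Allowing a generous 8-point excess in 8% of subjects shifts the mean by 0.64. With mean 15, z falls from 15/1.83 = 8.2 to 14.36/1.83 = 7.9, against a critical value of 1.96.

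**The case against.** The strongest reply is that most relapsers never reach this model. If the exit is recorded as lack of efficacy or an adverse event, the continuous endpoint is set to no change. Protocol 7.4.4 also requires at least three contact attempts, and efforts to obtain endpoint data from early withdrawals. What remains is a small group in which dependence of dropout on the diary may be weak. This largely stands, and is why the range includes an odds ratio of 1.3 and a missing share of 3%. It does not close the gap: the exit reason is recorded only if known. The no-change rule also covers only continuous endpoints, and SAP 5.6.4 does not say how lack-of-efficacy withdrawals are treated on the 10-point responder endpoint.

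A second reply is that the simulated cure is partly built in, because missingness was made to depend on the diary that is then added. That is fair. The simulation shows what the diary corrects if it drives dropout; it does not show that it does.

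A reader might also infer more than the documents support:
- That a good Month 3 score is carried forward. It is not: the plan makes 100 imputed data sets under a model that also includes age and site.
- That two label claims are at risk. The mean-change test is too far from its threshold.
- That the Table 9 schedule is a defect. It is not; the omission is in the SAP variable list.

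**Conclusion.** The point holds as a limitation of the ICIQ-OABqol imputation model in SAP 5.6.4. For scores missing for other reasons, nothing observed after Month 3 enters, although relevant diaries exist. If worse late diaries make missingness more likely, the imputed outcomes are too favourable. That condition is an assumption, so the favourable direction is conditional.

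The size is illustrative. With SD 20, correlation 0.4–0.6, mean change 15–25 and odds ratio 1.3–3.3 per SD, the 10-point response in missing subjects is overstated by about 2 to 15 percentage points, or roughly 0.1 to 1.4 responders of 120 at 3 to 8% missing. None of these inputs is given in the documents. Mean change matters: at 15 the overall 10-point response is Φ(5/20) = 60%, exactly at the 72 of 120 threshold; at 25 it is Φ(15/20) = 77%, well clear. A changed conclusion is therefore conceivable only for the responder test, within one or two responders of its threshold. The mean-change test would not plausibly change, and the primary endpoint is unaffected because its model already uses the diary counts.

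**What to change.** In SAP 5.6.4, add two auxiliary variables to the ICIQ-OABqol imputation model: baseline UUI episodes, and the UUI count from the last available diary through the endpoint visit (Month 6, or Month 12 for Month 12 outcomes). This costs one line of SAP text, two extra parameters and minor programming, with no new data. It is optional rather than essential, but there is little reason not to do it.

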# 7.5.9.17 Equipment for Assessment

Prior to enrollment of a subject, the sponsor shall ensure that all products from the Neuspera Implantable SNS System are available for the investigator. If updates for the Patient Controller, Clinician Programmer, or Wireless Transmitter are available, the Sponsor shall ensure these updates are provided to the devices of the investigator and the investigator is instructed on how to update the Patient Controller and Wireless Transmitter on the next follow-up visit of each subject.

Equipment used for study assessments, outside of the Neuspera SNS System, are maintained according to the institute's standard operation procedures and hospital procedures.

# 7.5.9.18 Factors that may Compromise the Outcome of the Clinical Trial or the Interpretation of Results

Any known or foreseeable factors that may compromise the outcome of the clinical trial or the interpretation of results are, to the best of the Sponsor's knowledge, obviated by the inclusion and exclusion criteria, the clinical investigational plan, and careful definition of clinical investigation procedures and outcome analyses.

Protocol no: NSM-004; Version 21.0 Page 101 of 141 04 Apr 2025
Confidential Neuspera

# 8 ADVERSE EVENTS, ADVERSE DEVICE EFFECTS AND DEVICE DEFICIENCIES

#### 8.1 Definitions

#### 8.1.1 Adverse Events

An adverse event (AE) is defined as any untoward medical occurrence, unintended disease or injury, or any untoward clinical signs, including an abnormal laboratory finding, in subjects, users or other persons, in the context of a clinical investigation, whether or not related to the investigational device. Definitions here are compatible with Regulation (EU) 2017/745 of the European Parliament.

This definition includes events that are anticipated as well as unanticipated events. This definition includes events occurring in the context of a clinical investigation related to the investigational device or the procedures involved. For the purpose of safety reporting all activities related to the use of a medical device may be considered procedures.

Any signs or symptoms associated with the reason for device replacement or explant should be reported as an adverse event (e.g. loss of stimulation).

Note: Because the protocol requires surgical procedures, mild pain, swelling, etc. should not be considered untoward and not considered an AE; however, any event that is more severe or lasts longer than typical should be considered an AE.

Subjects in the study, by definition, have UUI. Unless the UUI is worsened (more frequent or more severe), then UUI should not be considered untoward and should not be considered an AE.

Subjects may experience unpleasant sensations during the course of the device programming procedures. If the condition resolves immediately with re-programming, then these events should not be considered as untoward and are not AEs. Similarly, ongoing paresthesias should not be considered an AE unless they are bothersome to the subject.

#### 8.1.2 Serious Adverse Event

A serious adverse event (SAE) is defined as an AE that led to any of the following:

- a) Death,
- b) Serious deterioration in the health of the subject, that resulted in any of the following;
  - 1) Life-threatening illness or injury, or
  - 2) Permanent impairment of a body structure or a body function, or
  - 3) Hospitalization or prolongation of hospitalization, or
  - 4) Medical or surgical intervention to prevent life-threatening illness or injury or permanent impairment to a body structure or a body function,
  - 5) Chronic disease,
- c) Fetal distress, fetal death or a congenital physical or mental impairment or birth defect.

**NOTE:** Planned hospitalization for a pre-existing condition, or a procedure required by the study protocol, without serious deterioration in health, is not considered a serious adverse event.

In addition, per the FDA website:

Protocol no: NSM-004; Version 21.0 Page 102 of 141 04 Apr 2025
Confidential Neuspera

#### https://www.fda.gov/safety/reporting-serious-problems-fda/what-serious-adverse-event -

Other Serious (Important Medical Events) should be reported as a serious adverse event if the event does not fit the other outcomes cited above, but the event may jeopardize the subject and may require medical or surgical intervention (treatment) to prevent one of the other outcomes cited above.

### 8.1.3 Device Deficiency

Any inadequacy in the identity, quality, durability, reliability, safety or performance of an investigational device, including malfunctions, use errors, and inadequacy of information supplied by the manufacturer.

#### Malfunction

Failure of an investigational medical device to perform in accordance with its intended purpose when used in accordance with the instructions for use or clinical study protocol.

#### **Use Error**

Act or omission of an act that results in a different medical device response than intended by the manufacturer or expected by the user.

#### Inadequacy of Information Supplied by the Manufacturer.

Failure of an investigational medical device to perform in accordance with its instructions for use or visually not conform to the labeled device description.

#### 8.1.4 Serious Public Health Threat

A serious public health threat means an event which could result in imminent risk of death, serious deterioration in a person's state of health, or serious illness, that may require prompt remedial action, and that may cause significant morbidity or mortality in humans, or that is unusual or unexpected for the given place and time.

#### 8.1.5 Adverse Device Effect

An adverse device effect is an adverse event related to the use of an investigational medical device.

This definition includes adverse events resulting from insufficient or inadequate instructions for use, deployment, implantation, installation, or operation, or any malfunction of the investigational medical device. This definition includes any event resulting from use error or from intentional misuse of the investigational medical device.

